2.4.4 Analyses of efficacy endpoints

The primary and secondary efficacy endpoints will be analyzed using the ITT population. For patients who reduced dose to sarilumab 150mg during the course of the study, a listing of key efficacy endpoint variables will be provided.

Tipping point analysis will be performed. The number of responders to impute in each treatment group will vary from zero to up to the total number of patients with missing primary endpoint outcomes. For each imputation combination, a p-value based on Fisher's exact test will be calculated. The goal is to identify scenarios leading to non-significant results (p-value ≥ 0.05).

Patients who receive rescue therapy will be considered as non-responders. Withdrawn patients who had a disease flare prior to withdrawal will also be considered as non-responders as this represents the true outcome had they remained in the study. Withdrawn patients who did not experience a disease flare prior to withdrawal will be considered as missing and will be sequentially imputed for the tipping point analysis.

Subgroup analyses: To assess the consistency in treatment effects across subgroup levels, subgroup analyses will be conducted for the primary endpoint with respect to:

- Gender (Male versus Female)
- Race (Caucasian/White versus all other races)
- Region (Region 1 [Western countries], Region 2 [South America], Region 3 [Rest of the world])
- Age (<70, ≥ 70)
- Baseline weight (<60, ≥ 60 and <100, ≥ 100 kg)
- BMI (<25, ≥ 25 and <30, ≥ 30 kg/m²)
- Baseline CRP (\leq median, >median)
- Baseline ESR (\leq median, >median)
- Baseline CS dose (\leq median, >median)
- Number of relapses prior to screening (1, > 1 relapse)
- COVID-19 impacted population (Yes, No) – will only be performed if >10% of patients were impacted by COVID-19. The population without trial impact (disruption) due to COVID-19 is defined as patients without any critical or major deviation related to COVID-19 or did not permanently discontinue study treatment due to COVID-19.

Within each subgroup, the number and proportion of patients achieving sustained remission at Week 52 by treatment groups will be presented together with the proportion difference between sarilumab and placebo groups and its 95% confidence interval.

Subgroup analyses will also be performed with logistic regression models for binary status of patients achieving sustained remission at Week 52, with treatment group, subgroup variable and the subgroup-by treatment interaction as covariates. A p-value for the test of interaction will be provided.

Forest plots of treatment differences (proportion difference) between sarilumab and placebo at Week 52 and corresponding CIs for each subgroup will be provided.

2.4.4.2 Analyses of secondary efficacy endpoint(s)

Components of sustained remission composite measure at Week 52

Descriptive statistics (i.e., counts and percentages) will be provided for the following binary variables by treatment groups:

- Patients who achieve disease remission by Week 12
- Patients who have absence of disease flare from Week 12 through Week 52
- Patients who have normalization of CRP (decrease to <10 mg/L) with sustained normalization from Week 12 through Week 52
- Patients who successfully adhere to the prednisone taper from Week 12 through Week 52

Total cumulative corticosteroid (including prednisone) dose

Descriptive statistics including the number of subjects, mean, and median of the total cumulative prednisone (or equivalent) dose will be presented for each treatment group. The difference between the medians and the corresponding 95% non-parametric confidence interval along with p-value from the non-parametric Wilcoxon rank-sum test between the treatment groups will also be provided.

Both expected and actual cumulative CS dose will be presented. The expected cumulative dose is based on CS tapering regimen up to end of treatment, assuming that the taper was continued without error while actual cumulative CS dose will be calculated as the total cumulative CS used for PMR disease up to the end of treatment, including expected prednisone in tapering regimen per protocol, add-on prednisone, CS used in rescue therapy and the use of commercial prednisone. Patients who received increased prednisone or equivalent in rescue therapy will be included in their original treatment groups.

In the scenario that a patient has already taken external CS for the disease before randomization on the day of randomization, the CS dose taken will be considered as the first dose of oral IMP. The first dose of prednisone per tapering regimen will be skipped, and the patient will take the second dose of prednisone on the next day.

Time to first PMR flare during the treatment period

Time (from randomization) to the first PMR flare after clinical remission up to Week 52 will be analyzed by Kaplan-Meier method providing the median, 25th and 75th percentiles (where possible) along with the 95% CI for the median. The comparison between the treatment groups will be performed using Cox proportional hazards model. Hazard ratio and the corresponding 95% CI and p-value will be provided.

Composite GTI and Specific List

GTI analyses

Descriptive statistics including number, mean, SD, SE, median, minimum, and maximum will be provided by treatment group and by visit for domain-specific GTI score, composite GTI total score, composite worsening score and composite improvement score. For CWS and AIS at Week 52, analysis of covariance (ANCOVA) model with treatment groups and baseline glucocorticoid toxicity score as fixed effects, will be used to test the difference of the least-square means (LS means) between the treatment groups. Difference in LS means and the corresponding 95% CI along with the p-value will be provided.

In addition, descriptive statistics (i.e., counts and percentages) will be provided for not worsening (CWS = 0), worsening (CWS > 0), improved (AIS < 0) and not improved (AIS ≥ 0) at Week 52. Odds ratios and exact 95% CIs of not worsening versus worsening and improved versus not improved will be provided for the comparison between the sarilumab and placebo groups.

Analyses of items in Specific list

Number and percentage of patients with each item in specific list will be summarized by treatment groups and by visit.

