## **8.2 NONINVESTIGATIONAL MEDICINAL PRODUCT(S)**

### **Prednisone for rescue therapy**

If a patient experiences a disease flare or cannot adhere to the per protocol prednisone tapering schedule including the 5mg prednisone add-on prior to Week 12, then the patient must stop the per protocol prednisone taper and instead may receive commercial CS as a form of rescue therapy, per investigator's clinical judgment. The commercial CS will be reimbursed by the Sponsor. The patient should continue in the double-blind period of the study for the full 52 weeks and should continue to receive blinded sarilumab or matching placebo injections unless contraindicated by safety concerns and complete the remainder of the study assessments.

Once the patients are on the rescue therapy at the discretion of investigators, it is not allowed for them to return to per protocol prednisone taper regimen.

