#### **9.2.1.2 Total cumulative corticosteroid (including prednisone) dose over 52 weeks**

The total cumulative prednisone (or equivalent) dose over the 52-week period for each group will be analyzed as a secondary endpoint.

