2.4.3.2 Compliance

A given administration will be considered noncompliant if the patient did not take the planned dose of treatment as required by the protocol. No imputation will be made for patients with missing or incomplete data.

Percentage of compliance for SC IMP will be defined as the number of administrations the patient was compliant divided by the total number of administrations the patient was planned to take on or before the last dose date during the DB treatment period.

Percentage of compliance for oral IMP compliance rate will be defined as the total number of days patient with partial or complete oral IMP intake divided by total number of days between the first oral IMP intake date and day prior to rescue therapy start date or EOT date which is earlier.

Treatment compliance percentages will be summarized descriptively as quantitative variables (number, mean, SD, median, minimum, and maximum). The percentage of patients whose compliance is $<80\%$ will be summarized.

Cases of overdose (administering two or more doses of sarilumab or its matching placebo in less than 11 calendar days) will constitute AESI and will be listed as such. More generally, dosing irregularities will be listed in [Section 2.2.1](#).

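### SAP 2.4.4.2 builds the actual cumulative steroid dose from the uninterrupted taper plus rescue steroid with no cut-off at rescue; read literally, it counts doses not taken, mostly on placebo

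*SAP*

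**What the plan says.** SAP 2.4.4.2 presents two totals for each patient. The first is defined this way: "The expected cumulative dose is based on CS tapering regimen up to end of treatment, assuming that the taper was continued without error". The second follows in the same sentence: the "actual cumulative CS dose will be calculated as the total cumulative CS used for PMR disease up to the end of treatment, including expected prednisone". Its components are listed as "including expected prednisone in tapering regimen per protocol, add-on prednisone, CS used in rescue therapy and the use of commercial prednisone". No date is given at which the taper component stops for a rescued patient. The endpoint definition in SAP 2.1.3.2 lists the per-protocol taper beside add-on, commercial and rescue steroid, again without a stop date.

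Protocol 8.2 says what happens at rescue. If a patient flares or cannot keep to the taper, "then the patient must stop the per protocol prednisone taper and instead may receive commercial CS as a form of rescue therapy". After that, "it is not allowed for them to return to per protocol prednisone taper regimen". On follow-up: "The patient should continue in the double-blind period of the study for the full 52 weeks".

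The SAP does use a rescue cut-off in one place. The denominator for oral study-drug compliance in SAP 2.4.3.2 ends at the "day prior to rescue therapy start date or EOT date which is earlier".

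The planned outputs in SAP 2.4.4.2 are the mean and median per arm, the difference in medians with a non-parametric 95% confidence interval, and a Wilcoxon rank-sum p-value. SAP 2.4.4.4 names this endpoint, and no other secondary endpoint, as the one tested after the primary.

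**The concern.** Having just defined the expected dose as an uninterrupted taper, the SAP makes expected prednisone a component of the actual dose. On that wording the actual dose can never be lower than the expected dose. A rescued patient is credited with the rest of a taper that the protocol required them to stop, and also with the rescue steroid that replaced it. Because rescued patients normally stay in the double-blind period to Week 52, end of treatment does not act as a cut-off at rescue.

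The double count is uneven between arms. The sarilumab taper ends after Week 13 and the placebo taper runs through Week 51, so most of the surplus falls on placebo. That makes sarilumab look more steroid-sparing than the steroid taken would show. Protocol 9.8 describes reduction of cumulative steroid dose as central to judging a new PMR treatment, so the reported size of this effect matters.

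**Working it through.** The documents state no cumulative-dose total to reproduce, so the check starts from the taper table (Protocol Appendix A, repeated in SAP Appendix B).

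**Scheduled totals.** Sum of daily doses over Weeks 0–51, times 7:
- sarilumab arm: 111 × 7 = 777 mg
- placebo arm: 292 × 7 = 2044 mg
- scheduled difference: 2044 − 777 = 1267 mg

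**Surplus per rescued patient.** This is 7 × the sum of the scheduled daily doses from the rescue week to Week 51, which is what the literal rule counts and the patient did not take. Example for rescue at Week 12: sarilumab 7 × (2 + 1) = 21 mg; placebo 7 × 156 = 1092 mg.

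| Rescue at start of | Sarilumab (mg) | Placebo (mg) |
|---|---|---|
| Week 4 | 385 | 1652 |
| Week 8 | 147 | 1344 |
| Week 12 | 21 | 1092 |
| Week 16 | 0 | 868 |
| Week 24 | 0 | 504 |

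For rescue in the same week the placebo surplus is always the larger, and from Week 14 it falls on placebo alone. This follows from the schedule and needs no assumption.

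**Effect on the arm means.** The documents give no rescue rates, timing or doses. If rescue is spread evenly over Weeks 8–40 (assumed), the mean surplus per rescued patient is 11.9 mg on sarilumab and 585.5 mg on placebo. If 30% of each arm is rescued, the reported means rise by 0.30 × 11.9 = 4 mg and 0.30 × 585.5 = 176 mg. At 50% they rise by 6 mg and 293 mg. Rescue doses do not enter, because both counts include them.

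**Effect on the planned difference in medians.** Simulation with 59 per arm, rescue week uniform over 8–40, total rescue dose normal with mean 500, 1000 or 1500 mg (SD 300, floor 100 mg), 2000 runs per scenario. All of these are assumptions.

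| Share rescued, sarilumab / placebo | Median difference at mean 1000 mg: stopped at rescue → literal | Change over the three doses |
|---|---|---|
| 30 / 30% | 1267 → 1267 mg | −1% to 0% |
| 40 / 40% | 1233 → 1258 mg | 0% to +4% |
| 45 / 45% | 1144 → 1253 mg | +2% to +18% |
| 30 / 50% | 1271 → 1548 mg | +6% to +31% |
| 50 / 50% | 995 → 1276 mg | +6% to +47% |

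At 20/20% and 50/30% the change is also −1% to 0%, and at 30/40% it is 0% to +4%. The reason is simple. Unrescued placebo patients sit at exactly 2044 mg under either count, and they hold the median until close to half the arm is rescued. Near 50% the sample median flips between rescued and unrescued patients, so those rows are averages over unstable runs.

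**Effect on the test.** In these scenarios the Wilcoxon test rejects in at least 98% of runs under both counts.

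**A harsher set of assumptions.** Rescue was spread over Weeks 2–51, with daily rescue dose declining to zero over 24 weeks (200 runs per scenario). The weakest case had 60% of sarilumab and 30% of placebo rescued at the highest starting dose tried, 20 mg/day. The test rejected in 84% of runs with the cut-off and 90% on the literal count. With more than half of sarilumab rescued, the median difference fell under the literal count (305 to 264 mg in that case), so overstatement of the medians is not universal.

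**The case against.** The best defence is that the governing phrase speaks of steroid *used* for PMR, that the list after it only itemises what was used, and that a patient who has stopped the taper has no further per-protocol prednisone to use. The SAP also separates expected from actual dose, and its compliance rule shows that its authors knew oral dosing ends at rescue. A sensible programmer might well stop the taper at rescue. That stands: the text is ambiguous, and a reader should not infer that the dose was in fact derived wrongly. It does not remove the problem. The same sentence defines the word expected as uninterrupted, and the compliance cut-off is not extended to dose.

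It also stands that the test and, at low to moderate rescue, the planned median difference hardly change. A reader might infer that the testing sequence is compromised, or that the treatment estimate is generally inflated. The documents support neither. No difference in means is planned, so the shift in arm means affects a descriptive summary. The planned placebo response of 5–15% in Protocol 11.1 gives no rescue rate either: Protocol 11.4.2.1 also counts patients without remission, withdrawals and missing data as non-responders.

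A reader might also see a conflict over the counting window. Protocol 9.2.1.2 says "The total cumulative prednisone (or equivalent) dose over the 52-week period for each group will be analyzed as a secondary endpoint", whereas SAP 2.4.4.2 counts to end of treatment. SAP Appendix D refers to the 52-week treatment period, which fits either and is not a contradiction. The window matters only for patients who stop treatment permanently, and its direction is unknown.

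**Conclusion.** The point holds as a self-contradictory derivation rule that should be corrected. Followed literally, it counts taper doses not taken: per placebo patient, 1652 mg for rescue at Week 4, falling to 504 mg at Week 24; per sarilumab patient, 385 mg at Week 4 and nothing from Week 14. These figures rest only on the taper table and on rescued patients staying to Week 52.

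The consequence for results depends on rescue rates and doses that the documents do not give. The reported placebo mean rises with any rescue. Under the assumed scenarios, the difference in medians is essentially unchanged up to about 40% placebo rescue and is overstated only near 45–50% or more. The Wilcoxon decision is essentially unaffected. What is at risk is the reported size of steroid sparing, for the one secondary endpoint named in the testing sequence.

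**What to change.** In SAP 2.4.4.2, and to match in 2.1.3.2, state that the actual dose counts the scheduled taper only up to the day before rescue start or permanent stop of the oral study drug, whichever is earlier. The add-on, rescue and commercial steroid taken is then added. The rescue part of this cut-off is already in SAP 2.4.3.2.

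The cost is SAP wording and derivation code. The data exist: SAP 2.1.3.1 identifies rescue from the steroid page, and SAP 2.1.2 says all steroids taken during the study are reported. If the programming already stops at rescue, the change only documents that. The downside is that the reported steroid-sparing effect may be smaller. Scheduled doses missed before rescue would still be counted as taken, and the SAP should say so.

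Two optional clarifications could go in with the same edit. One is whether counting runs to Week 52 or to end of treatment for permanent discontinuers. The other is whether prednisone given for adverse events unrelated to PMR is included: SAP 2.1.3.2 includes it, while SAP 2.4.4.2 opens with steroid used for PMR.

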2.4.4.3 Analyses of exploratory endpoint(s)

Descriptive statistics will be provided for PMR-AS and its components at baseline, Week 12, Week 24, and Week 52.

The change from baseline at Week 52 for PMR-AS will be analyzed with mixed model repeated measures (MMRM) approach. The repeated-measures analysis will be based on the restricted maximum likelihood method assuming an unstructured covariance structure to model the within-subject errors. The model, including treatment, visit, and treatment -by -visit interaction, baseline and baseline -by -visit interaction as covariates, will be used to test the difference of least square means (LS means) between treatment groups in the change from baseline for PMR-AS at Week 52. The difference in LS means between treatment groups, the corresponding 95% CI and the p-value will be provided. No imputations will be performed for missing values.

Change from baseline at each visit will be plotted by treatment group for PMR-AS.

2.4.4.4 Multiplicity issues

If the primary endpoint reaches statistical significance, the secondary endpoint for total cumulative CS dose will be tested next.

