### **11.4.2 Analyses of efficacy endpoints**

#### **11.4.2.1 Analysis of primary efficacy endpoint(s)**

The primary endpoint (refer to [Section 9.1.1](#)) is the proportion of patients achieving sustained remission at Week 52 compared between sarilumab and placebo analyzed in the ITT population. The primary endpoint will be summarized as counts and proportions in each treatment group and analyzed by Fisher's exact test. Patients who do not achieve remission, receive rescue treatment with open label prednisone (or equivalent), withdraw from the study before Week 52, or having missing data that prevents assessment of the primary endpoint will be considered as non-responders. The significance level for all tests will be 0.05 (2-sided).

Sensitivity analyses will be performed based on a revised remission definition excluding acute phase reactants.

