#### **11.4.2.3 Multiplicity considerations**

If the primary endpoint reaches statistical significance, then secondary endpoints will be tested in a fixed sequential order to maintain an overall type I error rate of 0.05. Details of the hierarchical testing approach will be specified in the statistical analysis plan.

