1.2.2 Secondary objectives

- To demonstrate the efficacy of sarilumab (14 week taper of CS) compared to placebo (52 week taper of CS) in patients with PMR with regards to:
 - Clinical responses (such as components of sustained remission, disease remission rates, time to first disease flare) over time.

- Cumulative CS (including prednisone) exposure.
- To assess the safety (including immunogenicity) and tolerability of sarilumab in patients with PMR.
- To measure sarilumab concentrations from serum of patients with PMR.
- To assess the effect of sarilumab on reducing glucocorticoid toxicity as measured by the composite glucocorticoid toxicity index (GTI) questionnaire.

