Appendix D Summary of statistical analyses

Endpoint	Analysis		Statistical	Supportive	Subgroup	Other
	Population	Primary Analysis	Method	Analysis*	Analysis*	Analyses*
Primary Endpoint						
Patients who achieved sustained remission at Week 52	ITT	Proportion of patients achieving sustained remission at Week 52	Fisher's exact test	Tipping point analysis and primary endpoint excluding acute phase reactants and excluding incorrectly diagnosed PMR patients.	Yes Subgroups: Gender, race, region, age, baseline weight, BMI, baseline CRP, baseline ESR, baseline CS dose, prior relapse, COVID-19 impacted population.	No
Secondary Endpoints						
Patients who achieved of disease remission by Week 12	ITT	Proportion of patients who achieved of disease remission by Week 12	Descriptive	No	No	No
Patients who have absence of disease flare from Week 12 through Week 52	ITT	Proportion of patients who have absence of disease flare from Week 12 through Week 52	Descriptive	No	No	No
Patients who have normalization of CRP (decrease to <10 mg/L) with sustained normalization from Week 12 through Week 52	ITT	Proportion of patients who have normalization of CRP (decrease to <10 mg/L) with sustained normalization from Week 12 through Week 52	Descriptive	No	No	No
Patients who successfully adhere to the prednisone	ITT	Proportion of patients who successfully adhere to the prednisone taper from Week 12 through Week 52	Descriptive	No	No	No

	Analysis		Statistical	Supportive	Subgroup	Other
Endpoint	Population	Primary Analysis	Method	Analysis*	Analysis*	Analyses*
taper from Week 12 through Week 52						
Total cumulative prednisone (or equivalent) dose	ITT	Total cumulative prednisone (or equivalent) dose over 52-week treatment period	Wilcoxon rank-sum test	No	No	No
Time to the first PMR flare after clinical remission up to Week 52	ITT	Time (from randomization) to the first GCA flare after clinical remission up to Week 52	Kaplan-Meier estimates and Cox proportional hazards model	No	No	No
Total composite GTI total score	ITT	Cumulative GTI scores (CWS and AIS) at Week 52	Analysis of covariance (ANCOVA) model	No	No	Summaries of domain specific scores and specific list events at Week 12, 24, 40 and 52.
PMR activity score	ITT	PMR-AS at Week 52	MMRM model	No	No	Summaries of PMR-AS and components at baseline, Week 12, 24, and 52.
SF-36, EQ-5D-3L, FACIT-Fatigue, HAQ-DI, MD-VAS	ITT	Change from baseline at Week 52	MMRM model	No	No	No
Safety						

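### The SAP's testing sequence stops after cumulative CS dose, leaving three secondary endpoints with p-values outside the fixed order that the protocol promises

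*SAP*

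**What the plan says.** Protocol 11.4.2.3 makes secondary testing conditional on a significant primary endpoint and then states that "secondary endpoints will be tested in a fixed sequential order to maintain an overall type I error rate of 0.05". It leaves the details of the hierarchy to the SAP.

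SAP 2.4.4.4 is the section that should supply them. It is a single sentence: if the primary is significant, "the secondary endpoint for total cumulative CS dose will be tested next". Nothing follows.

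SAP 2.1.3.2 lists more secondary endpoints than that one: the components of sustained remission, time to first PMR flare, and the GTI scores CWS and AIS at Week 52. Under SAP 2.4.4.2:

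- The remission components are descriptive only.
- For time to first flare (Cox model), "Hazard ratio and the corresponding 95% CI and p-value will be provided".
- For CWS and AIS (ANCOVA), "Difference in LS means and the corresponding 95% CI along with the p-value will be provided".

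Time to first flare also belongs to the SAP 1.2.2 objective that begins "To demonstrate the efficacy of sarilumab (14 week taper of CS) compared to placebo". Protocol 11.4.2.1 sets a two-sided 0.05 level for all tests. SAP 1.5 and 1.6 do not list a shortened hierarchy among the changes, and SAP 1.6 states that the efficacy analysis plan is unchanged from the protocol.

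**The concern.** The protocol attaches an error guarantee to the secondary endpoints and delegates its mechanics to the SAP. The SAP supplies the mechanics for one endpoint and still tests three others. Those three have no position in the order, no stopping rule and no statement that their p-values are nominal. Elsewhere the SAP says so when it means descriptive, as for the remission components and the safety variables, so the silence here cannot safely be read as a label.

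At stake are the claims on disease control (flare) and steroid toxicity (CWS, AIS). As the SAP stands, a report could present any of them as a significant secondary result without the protection the protocol describes.

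**Working it through.** **Inputs.** Overall type I error 0.05 (protocol 11.4.2.3). Two-sided 0.05 per test (protocol 11.4.2.1). Secondary endpoints with a p-value but no place in the sequence: time to first flare, CWS and AIS, so k = 3 (SAP 2.1.3.2, 2.4.4.2, 2.4.4.4). Correlations between the test statistics are not in the documents and are assumed.

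**Step 1: the plan's own figure.** In a fixed sequence with every step at 0.05, a false positive requires rejecting the first true null hypothesis in the order. The family-wise error is therefore at most 0.05, which reproduces the protocol's figure. It also holds for the SAP's two-step sequence, primary then CS dose.

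**Step 2: the scenario that matters.** Because the protocol conditions secondary testing on the primary, no secondary error can occur under a global null unless the primary is itself a false positive, so that error stays at or below 0.05. The open case is a real primary effect together with a real CS-dose effect.

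The second of these is likely, because the CS-dose comparison is largely set by the assigned tapers (protocol Appendix A, SAP Appendix B). Adding the daily doses week by week and multiplying by 7 days:

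- Group 1: 111 × 7 = 777 mg
- Group 2: 292 × 7 = 2,044 mg

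Add-on and rescue prednisone can change this gap of 1,267 mg, but the step will seldom be what stops the sequence once the primary has succeeded.

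**Step 3: error among the three remaining tests.** Suppose flare, CWS and AIS have no true effect and each p-value is read at 0.05.

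- Independent: 1 − (1 − 0.05)³ = 1 − 0.857375 = 0.1426, or 14.3%.
- Upper bound under any dependence: 3 × 0.05 = 15%.
- Equal correlation r: Zᵢ = √r·C + √(1 − r)·Eᵢ with C and Eᵢ standard normal, and the error is P(max |Zᵢ| > 1.96), from 500,000 simulated draws.

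| Assumed r | At least one false positive among three | Ratio to 5% |
|---|---|---|
| 0 | 14.3% | 2.9 |
| 0.3 | 13.6% | 2.7 |
| 0.5 | 12.5% | 2.5 |
| 0.7 | 10.9% | 2.2 |
| 0.9 | 8.4% | 1.7 |

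CWS and AIS are built from the same nine domain scores, so some correlation between them is plausible. Every value in the table exceeds 5%.

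**Step 4: after the change.** With the three endpoints placed in order after CS dose, each at 0.05, the argument of Step 1 applies again and overall error is at most 0.05. The primary test, its power and the sample size are untouched.

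**The case against.** The best defence is that the protocol left the details to the SAP, and the SAP used that freedom: primary then CS dose is the confirmatory family, controlled at 0.05, and the rest is supportive. SAP 2.4.4.2 only says that p-values will be provided. It gives no significance level or decision rule and does not call these results confirmatory. The 0.05 for all tests stands in the protocol's section on the primary endpoint. Protocol 9.8 also describes the GTI as one of the other efficacy endpoints.

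Part of this stands. The inflation arises only if the three p-values are read at 0.05, and labelling them nominal is an acceptable answer. But the SAP does not say that, and SAP 1.6 declares the efficacy plan unchanged. Protocol 9.2.1.4 and SAP 2.1.3.2 both list the GTI as secondary.

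A reader might infer two stronger things, and the documents support neither.

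- **That the three tests run whether or not the primary succeeds.** Protocol 11.4.2.3 conditions secondary testing on the primary, and nothing in the SAP lifts that condition. Error rates computed under a global null with unconditional tests would overstate the problem.
- **That Appendix D enlarges the secondary family.** Under its Secondary Endpoints heading it lists the PMR activity score and a row for "SF-36, EQ-5D-3L, FACIT-Fatigue, HAQ-DI, MD-VAS". That is 18 further measures: PMR-AS 1, SF-36 10, EQ-5D 2, FACIT-Fatigue 1, HAQ-DI 3, MD-VAS 1. The body text classes PMR-AS as exploratory (SAP 2.1.3.3) and the others as other efficacy endpoints (SAP 2.1.8). A summary table does not reclassify them, so they should not be counted in the error rate. The heading is a labelling fault.

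**Conclusion.** The point holds as a gap between protocol and SAP. The order promised for the secondary endpoints is missing for three of them, and the omission is not declared. The primary analysis and the CS-dose test are not affected.

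The family-wise error among time to first flare, CWS and AIS is about 8% to 14%, against the stated 5%. This rests on three assumptions: the primary and CS-dose effects are real, the three endpoints have no true effect, and their p-values are read at two-sided 0.05. The range reflects assumed equal correlations from 0.9 down to 0. The change should be made, but it does not put the trial's main conclusion in doubt.

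**What to change.** Before unblinding, amend SAP 2.4.4.4 in one of two ways:

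1. Extend the fixed sequence after total cumulative CS dose to time to first flare, CWS at Week 52 and AIS at Week 52, in an order the sponsor fixes, each at two-sided 0.05 and stopping at the first non-significant result. This delivers what the protocol promises.
2. Label those three p-values nominal, with no significance claim, and record the departure from protocol 11.4.2.3 in SAP 1.6. The 0.05 then covers the primary and CS dose only.

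In either case, state that all other p-values are nominal, and re-head the PMR-AS and PRO/MD-VAS rows of Appendix D as exploratory or other, to match SAP 2.1.3.3 and 2.1.8.

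The cost is a few sentences and a re-headed block in one table, with no new data or analyses. Under the first option, a nominally significant result below a failed step can no longer be claimed. Under the second, none of the three can support a significance claim.
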